The best possible baseline values are the lowest value 0 for Pain VAS and PSS and the highest value 52 for FACIT-Fatigue scale. The worst possible post-baseline values are the highest values 100 and 16 for Pain VAS and PSS and the lowest value 0 for FACIT-Fatigue scale. Therefore, the maximum value for the worst possible change from baseline (i.e., the worst possible post-baseline value - best possible baseline value) is 100 for Pain VAS, 16 for PSS and -52 for FACIT-Fatigue scale.

The ranking rules are outlined in [Table 7.5:1](#).

Table 7.5: 1

Ranking rules for secondary continuous endpoint

	Category	Ranking	Case description	Imputed change from baseline for further ranking score*
1	Missing data at week 4 but still alive and no use of either escape medication, OL BI 655130 at D8 or rescue medication with BI 655130 prior to Week 4.	Ranked by imputed value	Patient has available data at visit prior to Week 4	LOCF prior to Week 4
			Patient has no post-baseline value	102 for Pain VAS 18 for PSS and -54 for FACIT-Fatigue scale
2	Use of escape medication, OL BI 655130 at D8 or rescue medication with BI 655130 prior to Week 4 but still alive.	Ranked by OL BI 655130 at D8 or time to rescue medication or time to escape medication from randomization;	Patient has OL BI 655130 at D8 and has no escape medication or rescue medication prior to Week 4;	104 for Pain VAS 20 for PSS and -56 for FACIT-Fatigue scale

Table 7.5: 1

Ranking rules for secondary continuous endpoint (cont'd.)

	Category	Ranking	Case description	Imputed change from baseline for further ranking score*
			Patient has rescue medication with BI 655130 x days from randomization and has no escape medication prior to Week 4;	106-x/1000 for Pain VAS 22-x/1000 for PSS and -58+x/1000 for FACIT-Fatigue scale
			Patient has escape medication y days after randomization and prior to Week 4;	108-y/1000 for Pain VAS 24-y/1000 for PSS and -60+y/1000 for FACIT-Fatigue scale
3	Patient died before the measurement at Week 4	Ranked by time to death from randomization	Patient died z days after randomization	110-z/1000 for Pain VAS 26-z/1000 for PSS and -62+z/1000 for FACIT-Fatigue scale

* Ranked values in this table are only for purpose of rank tests but not for any descriptive displays

With respect to safety evaluations, it is not planned to impute missing values.

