EN: Primary estimand for binary endpoint. For week 1, death or any use of escape medication, and, for week 4, death, or any use of escape medication, or OL Spesolimab use at D8, or any rescue medication with Spesolimab, prior to observing the endpoint(s) is considered to represent a non-response.

EN-PC: Alternative estimand for binary endpoint. For week 1, death or any use of escape medication, and, for week 4, death, or any use of escape medication, or OL Spesolimab use at D8, or any rescue medication with Spesolimab, prior to observing the endpoint(s) is considered to represent a non-response. Any data after the use of restricted medication for other purpose will be censored.

OC = observed cases excluding values after any use of escape medication, or OL Spesolimab use at D8, or any rescue medication with Spesolimab, OC-IR = observed cases including also values after any use of escape medication, or OL Spesolimab use at D8, or any rescue medication with Spesolimab.

"NRI", "BRI" and "EM" (Exhaustive method) mean analyses involving imputed data, cf. [Section 6.6.2](#).

Continuous efficacy endpoints for randomized dose at Day 1

For the primary estimand of continuous endpoints, death or any use of escape medication, or OL Spesolimab at Day 8, or any rescue medication with Spesolimab, prior to observing the endpoint(s) is considered to represent a non-response. Here the outcome of "non-response" itself is not a missing value but is the worst possible outcome of the corresponding

continuous endpoint. See [Section 7.5.2](#) for how to display continuous endpoint with both “non-response” outcome and other numeric continuous values.

The primary imputation strategy of missing values of continuous endpoints is LOCF after the implementation of estimand concept:

- Impute the missing outcome as the last available value (including baseline) prior to the missing outcome;

Wilcoxon rank test on secondary continuous endpoints:

For secondary continuous endpoints, a rank-based approach will be used for testing as below:

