The best possible baseline values are the lowest value 0 for Pain VAS score and PSS score, and the highest value 52 for FACIT-Fatigue scale score. The worst possible post-baseline values are the highest values 100 and 16 for Pain VAS score and PSS score respectively, and the lowest value 0 for the FACIT-Fatigue scale score. Therefore, the maximum value for the worst possible change from baseline (i.e., the worst possible post-baseline value – the best possible baseline value) is 100 for Pain VAS, 16 for PSS, and -52 for the FACIT-Fatigue scale. Furthermore, the maximum value for the worst percentage change from baseline in GPPASI at Week 1 and at Week 4 will be the highest observed percentage change from baseline of all patients with non-missing GPPASI at Week 1 or Week 4, which are denoted as PT1 and PT4 respectively.

For Wilcoxon rank tests of the secondary continuous endpoints at week 1 or at week 4, worst case ranks will be assigned to those patients with death, or prior escape medication, or OL Spesolimab at D8, or rescue medication with Spesolimab cf. Section 7.5 of CTP. The ranking rules for the tests are outlined in [Table 6.6.2: 2](#).

Table 6.6.2: 2 Ranking rules for Wilcoxon rank tests of secondary continuous endpoint on EN

	Category	Ranking	Case description	Imputed change from baseline for further ranking score
1	Missing data at week 1/4 ¹ but still alive and no use of either escape medication, OL Spesolimab at D8 or rescue medication with Spesolimab prior to Week 1/4 ¹ .	Rank by imputed value	Patient has available data at visit prior to Week 1/4 ¹	LOCF prior to Week 1/4 ¹
			Patient has no prior available value	102 for Pain VAS 18 for PSS and -54 for FACIT-Fatigue scale PT1/PT4+2 for percentage change from baseline in GPPASI at Week 1/4
2	Use of escape medication, OL Spesolimab at D8 or rescue medication with Spesolimab prior to endpoint collection at Week 1/4 ¹ but still alive.	Rank by OL Spesolimab at D8 or time to rescue medication or time to escape medication from randomized treatment.	Patient has OL Spesolimab at D8, and has no escape medication, and no rescue medication prior to endpoint collection at Week 4	104 for Pain VAS 20 for PSS -56 for FACIT-Fatigue scale PT4+4 for percentage change from baselines in GPPASI at Week 4

Table 6.6.2: 2 Ranking rules for Wilcoxon rank tests of secondary continuous endpoint on EN (cont'd.)

Category	Ranking	Case description	Imputed change from baseline for further ranking score*

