6.7 BASELINE, TIME WINDOWS AND CALCULATED VISITS

Baseline, unless otherwise specified, refers to the last measurement collected prior to the dose of randomized Spesolimab/placebo administered at Day 1 in the study. For the analysis of biomarkers (see [Section 7.6.5](#)) baseline refers to the last measurement prior to randomized treatment administered at Day 1 but not more than 5 days earlier.

Measurements reported with date and time and taken prior to start of administration of trial treatment will be considered pre-treatment values. Measurements reported with a date only (and no time) and taken on the day of administration of trial treatment will also be considered pre-treatment values. These pre-treatment values will be assigned to visits according to the nominal visit number as recorded on the eCRF or as provided by the laboratory.

Measurements taken after start of administration of trial treatment will be considered either on- or off-treatment values based on the definition in [Section 6.1](#), and will be assigned to visits for statistical analysis, if applicable, as defined below.

Analysis of AE data, concomitant medications, recurrence of flares and of rescue/escape medication use will not be based on visits therefore, no assignment to time windows will be necessary.

All other safety, efficacy [REDACTED] measurements will be assigned to visits based on time windows around the planned visit dates, defined relative to the day of first trial treatment, Day 1. These time windows are defined in [Table 6.7: 1](#).

Table 6.7: 1 Time windows for assignment of efficacy, safety lab, vital signs [REDACTED]
[REDACTED] to visits for statistical analysis

Visit number	Visit label	Planned day	Time window		
			Window (per CTP)	Start (extended)	End (extended)
2	Week 1, Day 1	Day 1	exact day	Day 1 ^A	Day 1 ^A
3	Week 1, Day 2	Day 2	exact day	Day 2	Day 2
4	Week 1, Day 3	Day 3	exact day	Day 3	Day 3
5 ^B	Week 1, Day 4	Day 4	exact day	Day 4	Day 4
6 ^B	Week 1, Day 5	Day 5	exact day	Day 5	Day 5
7 ^B	Week 1, Day 6	Day 6	exact day	Day 6	Day 6
8 ^B	Week 1, Day 7	Day 7	exact day	Day 7	Day 7
9 ^E	Week 1, Day 8	Day 8	exact day	Day 8	Day 10
10	Week 2	Day 15	+/- 3 days	Day 11	Day 18
11	Week 3	Day 22	+/- 3 days	Day 19	Day 25
12	Week 4	Day 29	+/- 3 days	Day 26	Day 43
13	Week 8	Day 57	+/- 7 days	Day 44	Day 71
14	Week 12 ^C	Day 85	+/- 7 days	Day 72	Day 99
Post Week 12 ^D				Day 100	Day 113
Off treatment ^D				Day 114	Day of last follow-up value

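### For baseline-only patients, the SAP's LOCF rule replaces the protocol's penalty score with a change of zero in three confirmatory rank tests

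*SAP*

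**What the plan says.** Protocol Section 7.5 covers patients who are alive, have had no escape medication, Day 8 open-label dose or rescue dose, and lack a Week 4 value. Table 7.5: 1 splits them in two. Those with data at a prior visit get LOCF. Those in the row "Patient has no post-baseline value" are scored "102 for Pain VAS 18 for PSS and -54 for FACIT-Fatigue scale". The same section gives the worst possible change, which "is 100 for Pain VAS, 16 for PSS and -52 for FACIT-Fatigue scale".

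SAP Section 6.6.2 states: "The primary imputation strategy of missing values of continuous endpoints is LOCF after the implementation of estimand concept". The bullet beneath it reads: "Impute the missing outcome as the last available value (including baseline) prior to the missing outcome". SAP Table 6.6.2: 2 repeats the protocol's two rows. The LOCF row is triggered by "Patient has available data at visit prior to Week 1/4", and the penalty row, with the same three scores, by "Patient has no prior available value". The SAP adds a line for percentage change in GPPASI (PT1/PT4+2) that the protocol table does not have.

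SAP Section 6.7 says baseline "refers to the last measurement collected prior to the dose of randomized Spesolimab/placebo", and its time-window table lists Day 1 as an analysis visit.

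**The concern.** The two documents give the same patient different scores in a confirmatory test. Under the protocol, a patient lost before any post-baseline questionnaire ranks below every patient with an observed change. Under the SAP taken literally, the patient ranks as unchanged, ahead of anyone who worsened.

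Such patients can occur. The flow chart collects Pain VAS and FACIT-Fatigue on Day 1 and next on Day 8, so a patient lost in the first week has only a baseline on those two scales. SAP Section 6.3 keeps randomized but untreated patients in the efficacy analysis.

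The tests are sequential at one-sided 0.025. A borderline Pain VAS result therefore also decides whether PSS and FACIT-Fatigue are tested, and the ranks should not depend on which document the programmer follows.

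**Working it through.** **1. The protocol's own figures.** Worst change = worst post-baseline value minus best baseline value. Each penalty lies 2 points beyond it.

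| Endpoint | Worst change | Protocol score, baseline only | SAP score, baseline only | Score for Day 8 open-label dose |
|---|---|---|---|---|
| Pain VAS | 100 - 0 = 100 | 102 | 0 | 104 |
| PSS | 16 - 0 = 16 | 18 | 0 | 20 |
| FACIT-Fatigue | 0 - 52 = -52 | -54 | 0 | -56 |

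The SAP score is baseline minus baseline. Under either rule the patient still ranks better than anyone with an intercurrent event, so only comparisons with event-free patients in the other arm who worsened can move.

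**2. Formula (Pain VAS).** Let f be the intercurrent-event proportion and p the probability that an event-free patient's change is above 0. Moving one patient from 102 to 0 shifts the Wilcoxon U by an expected

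- 17 × (1 - f placebo) × p placebo, for a spesolimab patient (favours the drug);
- 34 × (1 - f spesolimab) × p spesolimab, for a placebo patient (against the drug).

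SD of U without tie correction = √(34 × 17 × 52 / 12) = 50.05.

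**3. Inputs.** From the protocol: 34:17 allocation, and SD 32.3 for Pain VAS change (seven-patient trial, Week 2, Protocol Section 1.2.3). The mean changes and event proportions are assumptions.

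- Set A: SD 32.3, means -30 (spesolimab) and 0 (placebo). So p placebo = 0.50 and p spesolimab = P(Z > 30/32.3) = 0.1765.
- Set B: SD 32, means -45 and -15. So p placebo = P(Z > 15/32) = 0.320 and p spesolimab = P(Z > 45/32) = 0.080.

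**4. Shift in z, SAP rule minus protocol rule (positive favours spesolimab).**

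| Set; events spesolimab / placebo | One spesolimab patient | One placebo patient | Two spesolimab and one placebo |
|---|---|---|---|
| A; 35% / 85% | 17×0.15×0.50 = 1.28; +0.025 | 34×0.65×0.1765 = 3.90; -0.078 | -0.025 |
| A; 35% / 70% | 2.55; +0.051 | 3.90; -0.078 | +0.023 |
| A; 35% / 50% | 4.25; +0.085 | 3.90; -0.078 | +0.086 |
| B; 40% / 90% | 17×0.10×0.320 = 0.54; +0.011 | 34×0.60×0.080 = 1.63; -0.033 | -0.010 |
| B; 20% / 50% | 2.72; +0.054 | 34×0.80×0.080 = 2.17; -0.043 | +0.061 |

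In the last column, baseline-only patients tie with each other under both rules, so the counts drop to 16 and 32. First row: 2×16×0.15×0.50 - 32×0.65×0.1765 = 2.40 - 3.67 = -1.27, and -1.27/50.05 = -0.025. A tie-corrected simulation (4000 runs; all rows except A 35% / 70%) changed these shifts by no more than about 0.006.

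**5. Power, Set A, 2000 simulated trials, protocol rule v SAP rule.**

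| Placebo events | Two baseline-only on spesolimab | Two baseline-only on placebo |
|---|---|---|
| 85% | 98.0% v 98.5% | 95.8% v 93.6% |
| 70% | 80.1% v 83.8% | 78.4% v 72.4% |
| 50% | 40.3% v 49.3% | 44.8% v 38.2% |

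SAP Section 7.5.2 expects most placebo patients to have escape medication or the Day 8 open-label dose, so the 70% and 85% rows are nearer the plan.

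**The case against.** The strongest defence is that the SAP wording need not depart from the protocol. The phrase admitting baseline sits in a general LOCF bullet. The rank test has its own heading and table, whose trigger could be shorthand for no prior post-baseline value. That reading is possible, but the SAP gives it little support. The bullet is the only definition of LOCF for continuous endpoints, the words that excluded baseline were dropped from the table, Day 1 is a listed visit, and the best-response rule in the same section also counts baseline as available data.

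A reader might infer that the penalty has been switched off. It has not. The row and its scores remain, and they are assigned directly as an imputed change, so no baseline is needed to apply them. Patients without a baseline can exist, because Protocol Section 6.2 leaves questionnaires uncompleted when a patient is too sick even to answer verbally. The trigger is narrowed.

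A reader might also infer a tilt towards the drug. The table in the working shows the sign depends on the arm. With two spesolimab patients and one placebo patient, in line with 2:1 allocation, the net shift runs from -0.025 to +0.086.

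Two further points stand. The reach is narrow, especially for PSS, which is collected from Day 2, so one early value removes the problem. And non-declaration cannot be stated absolutely: the SAP history table records that the ranking rules were updated, and parts of Section 4 and its history entry are redacted.

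**Conclusion.** The conflict is real and minor. Taken literally, the SAP scores a baseline-only, event-free patient 0 where the protocol scores 102, 18 or -54, on three endpoints in the testing hierarchy. For the Wilcoxon ranks, the readable part of SAP Section 4 mentions only the Day 1 time origin.

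The per-patient effect could change only a borderline result. It rests on assumed mean changes and event proportions, an SD from seven patients, and an unknown number of baseline-only patients. The documents support neither a claim that the penalty was removed nor a claim of overall bias towards spesolimab. What they support is that a confirmatory rank is specified in two incompatible ways.

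**What to change.** - In SAP Section 6.6.2 and Table 6.6.2: 2, restrict LOCF to post-baseline values for the rank tests and restore the protocol's trigger, no post-baseline value, for the 102 / 18 / -54 row.
- Apply the same trigger to the PT1/PT4+2 line for GPPASI. That line exists only in the SAP, so this is for consistency and does not restore a protocol rule.
- State in SAP Section 7.5.2 how baseline-only patients enter the modified Hodges-Lehmann estimate. It imputes by LOCF, while the penalty scores are for rank tests only, so changing the rank test alone would leave test and estimate treating the same patient differently.
- If carrying baseline forward was intended, declare and justify it in SAP Section 4 instead.

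The cost is a few phrases of SAP text. The downside is slightly less favourable ranks for early dropouts in either arm.

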Assignment of observations to visits based on time windows will be based on the non-imputed (observed) data after the implement of estimand concepts. For example, for EN estimand, values after death or use of escape medication, OL Spesolimab at Day 8 or rescue medication with Spesolimab should be set to be “Non-response” first before assignment of efficacy endpoints.

For visits without an assigned value based on time windows, a value will thereafter be imputed (if needed) as defined in [Section 6.6](#). Imputation of efficacy endpoints, when applicable, will be performed based on all available observations meeting the imputation rules, irrespective of whether the observation was selected in any time window.

Tables and figures presenting results of the statistical analysis will only display visits at which the respective parameter was planned to be collected according to the CTP. Note that Visits 5-8 are optional so they will not be displayed in tables and figures only if otherwise specified.

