Secondary endpoints not included in the testing procedure

[figure not shown]
For the binary secondary endpoints (either at week 1 or at week 4) that, are not included into the statistical testing strategy, graphical displays and statistical testing using the Suissa-Shuster Z-pooled test will be performed using the primary estimand and imputation strategy (EN-NRI), as described for the primary endpoint in [Section 7.4](#).

[figure not shown]
For the continuous secondary endpoints, the percentage change in GPPASI from baseline at Week 1 and Week 4, which are not included into the statistical testing strategy, the analysis will be performed using the same method as for the secondary continuous endpoints in the testing strategy. All details regarding the ranking rules for Wilcoxon rank tests are defined in [Section 6.6.2](#) (and [Table 6.6.2: 2](#)).

[figure not shown]

[figure not shown]

[figure not shown]

[figure not shown]

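### In SAP Table 6.6.2: 2 a carried-forward GPPASI percent change can rank worse than open-label use, rescue, escape or death, mainly at Week 4

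*SAP*

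**What the plan says.** SAP Section 6.6.2 states that death, escape medication, open-label spesolimab at Day 8 and rescue spesolimab take the worst ranks in the Wilcoxon tests. Table 6.6.2: 2 does this through scores placed beyond a worst value.

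For the three scales in the testing hierarchy, that worst value is the theoretical limit of change, which "is 100 for Pain VAS, 16 for PSS, and -52 for the FACIT-Fatigue scale". For percent change in GPPASI it comes from the data: it "will be the highest observed percentage change from baseline of all patients with non-missing GPPASI at Week 1 or Week 4", called PT1 and PT4. The GPPASI steps are:

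- no earlier value: "PT1/PT4+2 for percentage change from baseline in GPPASI at Week 1/4"
- open-label at Day 8: "PT4+4 for percentage change from baselines in GPPASI at Week 4"
- rescue on day x: PT4 + 6 − x/1000
- escape on day y: PT + 8 − y/1000
- death on day z: PT + 10 − z/1000

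A living patient with no intercurrent event who is missing at the visit is scored "LOCF prior to Week 1/4". The general LOCF rule is: "Impute the missing outcome as the last available value (including baseline) prior to the missing outcome". SAP Section 6.7 adds: "Imputation of efficacy endpoints, when applicable, will be performed based on all available observations meeting the imputation rules", whether or not the observation was selected in a visit window.

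SAP Section 7.5.2 places percent change in GPPASI at Weeks 1 and 4 outside the testing strategy, but "the analysis will be performed using the same method as for the secondary continuous endpoints in the testing strategy". The protocol's own ranking table (Table 7.5: 1) has no GPPASI entry; the SAP added it.

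**The concern.** A worst-rank analysis needs every penalty score to lie beyond every value that can be ranked as a measurement. For Pain VAS, PSS and FACIT-Fatigue this is guaranteed. For GPPASI it is guaranteed only against values observed at the visit. A carried-forward value belongs to a patient who is missing at the visit, so by definition it is not in the maximum that sets PT, and nothing caps it.

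If it lies far enough above PT, a patient who merely missed a visit, and who may have improved, ranks worse than patients who needed open-label drug, rescue or escape, or who died. The test then does not follow the order that the SAP states, and the shift can favour either arm, depending on whose patient is missing.

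**Working it through.** **1. The three hierarchy scales keep their order.** Worst post-baseline value minus best baseline value gives 100 − 0 = 100, 16 − 0 = 16 and 0 − 52 = −52, as the SAP states. For a death on Day 28 the scores are 110 − 0.028 = 109.972, 26 − 0.028 = 25.972 and −62 + 0.028 = −61.972. All lie beyond any possible carried-forward change (100, 16, −52), and the intermediate steps are also in order.

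**2. Condition for inversion in GPPASI.** Let L be the carried-forward percent change. The patient ranks worse than:

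- open-label Day 8 if L > PT4 + 4
- rescue if L > PT4 + 6 − x/1000
- escape if L > PT + 8 − y/1000
- death if L > PT + 10 − z/1000

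The full 10-point gap is 1 to 4 GPPASI points for baselines of 10 to 40 (assumed), since 0.10 × 10 = 1 and 0.10 × 40 = 4.

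**3. Example (assumed data).** Observed Week 4 changes are −95, −90, −85, −70 and −40, with one L = −10; events are on day 14.

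| | PT4 | No earlier value | Open-label | Rescue | Escape | Death | L = −10 |
|---|---|---|---|---|---|---|---|
| As written | −40 | −38 | −36 | −34.014 | −32.014 | −30.014 | worse than all |
| PT4 includes L | −10 | −8 | −6 | −4.014 | −2.014 | −0.014 | better than all |

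**4. Why Week 4.** Under the primary estimand, SAP Section 6.7 sets values after an intercurrent event to non-response before visits are assigned. SAP Section 7.5.2 expects most placebo patients to have had escape or open-label drug by Day 8. If such values do not count toward PT4 (the SAP does not say), PT4 comes mostly from responders. The proof-of-concept mean reduction in GPPASI at Week 4 was 82.0% (protocol Section 1.2.3).

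At Week 1, Table 6.7: 1 uses assessments made before any non-randomized treatment, so placebo patients without escape enter PT1. The open-label and rescue steps do not apply there.

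**5. How often, for an assumed L = 0%.** The death score is passed when PT < −10, ignoring z/1000. Take percent changes as normal, truncated at −100, with p the chance that one patient lies below −10; then P(PT < −10) = pⁿ.

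All observed patients responding like active patients:

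| Assumed mean, SD | p | n = 22 | n = 50 |
|---|---|---|---|
| −82, 16 | >0.9999 | >99% | >99% |
| −75, 25 | (0.9953 − 0.1587)/0.8413 = 0.9945 | 89% | 76% |
| −70, 30 | (0.9772 − 0.1587)/0.8413 = 0.9730 | 55% | 25% |

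Now 33 active patients (−82, SD 16.2, the SD borrowed from proof-of-concept Week 2), all below −10 with probability over 0.999, plus k observed placebo patients:

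| Assumed placebo mean, SD | p | k = 1 | k = 3 | k = 5 | k = 15 |
|---|---|---|---|---|---|
| 0, 25 | 0.345 | 34% | 4% | <1% | 0% |
| −40, 30 | (0.8413 − 0.0228)/0.9772 = 0.838 | 84% | 59% | 41% | 7% |
| −40, 25 | (0.8849 − 0.0082)/0.9918 = 0.884 | 88% | 69% | 54% | 16% |

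The k = 15 column resembles Week 1; the small-k columns resemble Week 4 with few placebo patients free of events. All are conditional on a patient with L = 0% being present.

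**6. Effect on the test.** With 34:17, the SD of the rank sum is √(34 × 17 × 52/12) = 50.05. One spesolimab patient passing 8 to 15 of 17 placebo non-responders (assumed) shifts it by 8/50.05 = 0.16 to 15/50.05 = 0.30 SD. One placebo patient passing 4 to 12 spesolimab non-responders (assumed) shifts it by 0.08 to 0.24 SD in the other direction.

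**The case against.** A reader might infer that a missing patient scored 0% from baseline would almost always rank below a death. The documents do not support that.

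- The score of a baseline-only patient is unsettled. The general LOCF rule allows baseline, giving 0%. The SAP table refers back to protocol Section 7.5, whose table gives the penalty to a patient with nothing after baseline; that means PT + 2 and no inversion against any intercurrent event.
- Carrying baseline to Week 4 would require no GPPASI assessment on Days 2, 3, 8, 15 or 22, nor anywhere in the Week 4 window to Day 43. The realistic case is a Day 8 to 22 value carried forward, whose size is unknown.
- The figures above 99% treat every observed patient as a responder, with a mean from a seven-patient, open-label, all-active study. One third of this trial is randomized to placebo, and even one placebo-like value lowers the figure.

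A reader might also infer that the worst-rank estimand fails as a whole, or that any missing patient is misplaced. Neither follows. Inversion needs L above the relevant step. The table's scores serve the rank tests only: the quartiles and the modified Hodges-Lehmann estimate treat non-response directly as the worst outcome, and the MMRM, censored-LOCF and observed-case displays do not use the scores. Amendment 1 of the protocol also says that death is not expected to matter here.

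All of this stands and limits the size. It does not remove the fault: no other passage caps the carried-forward value or brings it into PT.

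**Conclusion.** The rule as written can break the SAP's stated order. It does so whenever a patient missing without an intercurrent event carries forward a change above about PT + 4 (open-label Day 8), PT + 6 (rescue), PT + 8 (escape) or PT + 10 (death). In practice the comparison with open-label, rescue and escape patients matters more than the one with deaths, which may be few or none.

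It is mainly a Week 4 issue. It is less likely at Week 1, where up to 16% was found under the most favourable of the placebo assumptions tried and about zero under the least. No single frequency can be given for Week 4: it depends on whether post-event values count toward PT4, how many placebo-like values remain, and which value is carried.

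The reach is narrow: the Wilcoxon tests of percent change in GPPASI, outside the hierarchy. The primary, key secondary and hierarchical tests, and the type I error, are unaffected. It deserves correction because these are named secondary endpoints with a planned test.

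**What to change.** In SAP Section 6.6.2, define PT1 and PT4 as the maximum over all percent changes that enter the ranking as measurements at that visit, observed and LOCF-imputed alike, and then add the 2 to 10 point steps. This also settles whether values replaced by non-response count: they do not enter the ranking, so they do not enter PT.

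Alternatively, use one large constant above any attainable percent change. It cannot be read directly off the GPPASI maximum of 72, because the largest change is (72 − baseline)/baseline: +620% from a baseline of 10 but +80% from 40. Since the scores serve ranking only, the size of the constant does not matter once it is high enough.

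Align the table row for a patient lacking earlier data with the protocol's row for a patient lacking post-baseline data, so that a baseline-only patient has one score. The cost is one or two sentences and a small programming change, best made before unblinding. No other analysis changes.
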